14.3 Safety Data

14.3.1 Displays of Adverse Events

Table 387: Overall Summary of Adverse Events by Treatment Group - All Subjects

| Subjects ^a with | | Arm 2A (N=X) | | Arm 2B (N=X) | | Arm 2C (N=X) | | Arm 2D (N=X) | | Arm 2E (N=X) | | Arm 2F (N=X) | | Arm 2G (N=X) | | Arm 2H (N=X) | | All Subjects (N=X) | |
|---|--------------------|-----------------|---|-----------------|---|-----------------|---|-----------------|---|-----------------|---|-----------------|---|-----------------|---|-----------------|---|-----------------------|---|
| Category 1 | Category 2 | n | % | n | % | n | % | n | % | n | % | n | % | n | % | n | % | n | % |
| At least one local solicited adverse event | NA | | | | | | | | | | | | | | | | | | |
| At least one systemic solicited adverse event | NA | | | | | | | | | | | | | | | | | | |
| At least one unsolicited adverse event | NA | | | | | | | | | | | | | | | | | | |
| At least one related unsolicited adverse event | Any Grade | | | | | | | | | | | | | | | | | | |
| | Mild (Grade 1) | | | | | | | | | | | | | | | | | | |
| | Moderate (Grade 2) | | | | | | | | | | | | | | | | | | |
| | Severe (Grade 3) | | | | | | | | | | | | | | | | | | |
| At least one severe (Grade 3) unsolicited adverse event | Any relationship | | | | | | | | | | | | | | | | | | |
| | Related | | | | | | | | | | | | | | | | | | |
| | Unrelated | | | | | | | | | | | | | | | | | | |
| At least one serious adverse event ^b | Any relationship | | | | | | | | | | | | | | | | | | |

| Subjects ^a with | | Arm 2A (N=X) | | Arm 2B (N=X) | | Arm 2C (N=X) | | Arm 2D (N=X) | | Arm 2E (N=X) | | Arm 2F (N=X) | | Arm 2G (N=X) | | Arm 2H (N=X) | | All Subjects (N=X) | |
|--|------------|-----------------|---|-----------------|---|-----------------|---|-----------------|---|-----------------|---|-----------------|---|-----------------|---|-----------------|---|-----------------------|---|
| Category 1 | Category 2 | n | % | n | % | n | % | n | % | n | % | n | % | n | % | n | % | n | % |
| | Related | | | | | | | | | | | | | | | | | | |
| | Unrelated | | | | | | | | | | | | | | | | | | |
| At least one adverse event leading to early termination ^c | N/A | | | | | | | | | | | | | | | | | | |
| Any Vital Signs Adverse Event | N/A | | | | | | | | | | | | | | | | | | |
| At least one medically attended adverse event | N/A | | | | | | | | | | | | | | | | | | |
| At least one new onset chronic medical condition | N/A | | | | | | | | | | | | | | | | | | |

N = Number of subjects in the Safety Population

^aSubjects are counted once for each category regardless of the number of events.

^bA listing of Serious Adverse Events is included in Table 157.

^cAs reported on the Adverse Event eCRF.

Table 388: Serious Adverse Events and Non-Serious Adverse Events Occurring in 5% of Subjects in Any Treatment Group by MedDRA System Organ Class and Preferred Term, and Treatment Group - All Subjects

| Preferred Term | MedDRA System Organ Class | Arm 2A (N=X) | | | Arm 2B (N=X) | | | Arm 2C (N=X) | | | Arm 2D (N=X) | | | Arm 2E (N=X) | | | Arm 2F (N=X) | | | Arm 2G (N=X) | | | Arm 2H (N=X) | | | All Subjects (N=X) | | |
|--|---------------------------|--------------|---|--------|--------------|---|--------|--------------|---|--------|--------------|---|--------|--------------|---|--------|--------------|---|--------|--------------|---|--------|--------------|---|--------|--------------------|---|--------|
| | | n | % | Events | n | % | Events |
| Serious Adverse Events | | | | | | | | | | | | | | | | | | | | | | | | | | | | |
| All | All | x | x | x | x | x | x | x | x | x | x | x | x | x | x | x | x | x | x | x | x | x | x | x | x | x | x | x |
| PT1 | SOC1 | x | x | x | x | x | x | x | x | x | x | x | x | x | x | x | x | x | x | x | x | x | x | x | x | x | x | x |
| Etc. | Etc. | | | | | | | | | | | | | | | | | | | | | | | | | | | |
| Other (Non-serious) Adverse Events | | | | | | | | | | | | | | | | | | | | | | | | | | | | |
| All | All | x | x | x | x | x | x | x | x | x | x | x | x | x | x | x | x | x | x | x | x | x | x | x | x | x | x | x |
| PT1 | SOC1 | x | x | x | x | x | x | x | x | x | x | x | x | x | x | x | x | x | x | x | x | x | x | x | x | x | x | x |
| Etc | Etc | | | | | | | | | | | | | | | | | | | | | | | | | | | |
| N = number of subjects in the Safety Population (number of subjects at risk). n= number of subjects reporting event. Events= total frequency of events reported. | | | | | | | | | | | | | | | | | | | | | | | | | | | | |

14.3.1.1 Solicited Adverse Events

Table 389: Number and Percentage of Subjects Experiencing Solicited Events by Symptom, Maximum Severity, and Treatment Group

| Symptom | Severity | Arm 2A (N=X) | | Arm 2B (N=X) | | Arm 2C (N=X) | | Arm 2D (N=X) | | Arm 2E (N=X) | | Arm 2F (N=X) | | Arm 2G (N=X) | | Arm 2H (N=X) | | All Subjects (N=X) | | |
|----------------------|----------|-----------------|---|-----------------|---|-----------------|---|-----------------|---|-----------------|---|-----------------|---|-----------------|---|-----------------|---|--------------------------|---|--|
| | | n | % | n | % | n | % | n | % | n | % | n | % | n | % | n | % | n | % | |
| Any Symptom | None | | | | | | | | | | | | | | | | | | | |
| | Mild | | | | | | | | | | | | | | | | | | | |
| | Moderate | | | | | | | | | | | | | | | | | | | |
| | Severe | | | | | | | | | | | | | | | | | | | |
| Any Systemic Symptom | None | | | | | | | | | | | | | | | | | | | |
| | Mild | | | | | | | | | | | | | | | | | | | |
| | Moderate | | | | | | | | | | | | | | | | | | | |
| | Severe | | | | | | | | | | | | | | | | | | | |
| Arthralgia | None | | | | | | | | | | | | | | | | | | | |
| | Mild | | | | | | | | | | | | | | | | | | | |
| | Moderate | | | | | | | | | | | | | | | | | | | |
| | Severe | | | | | | | | | | | | | | | | | | | |
| Fatigue | None | | | | | | | | | | | | | | | | | | | |
| | Mild | | | | | | | | | | | | | | | | | | | |
| | Moderate | | | | | | | | | | | | | | | | | | | |
| | Severe | | | | | | | | | | | | | | | | | | | |
| Fever ^a | None | | | | | | | | | | | | | | | | | | | |
| | Mild | | | | | | | | | | | | | | | | | | | |
| | Moderate | | | | | | | | | | | | | | | | | | | |
| | Severe | | | | | | | | | | | | | | | | | | | |

| | | Arm 2A (N=X) | | Arm 2B (N=X) | | Arm 2C (N=X) | | Arm 2D (N=X) | | Arm 2E (N=X) | | Arm 2F (N=X) | | Arm 2G (N=X) | | Arm 2H (N=X) | | All Subjects (N=X) | |
|-------------------|----------|-----------------|---|-----------------|---|-----------------|---|-----------------|---|-----------------|---|-----------------|---|-----------------|---|-----------------|---|--------------------------|---|
| Symptom | Severity | n | % | n | % | n | % | n | % | n | % | n | % | n | % | n | % | n | % |
| Feverishness | None | | | | | | | | | | | | | | | | | | |
| | Mild | | | | | | | | | | | | | | | | | | |
| | Moderate | | | | | | | | | | | | | | | | | | |
| | Severe | | | | | | | | | | | | | | | | | | |
| Headache | None | | | | | | | | | | | | | | | | | | |
| | Mild | | | | | | | | | | | | | | | | | | |
| | Moderate | | | | | | | | | | | | | | | | | | |
| | Severe | | | | | | | | | | | | | | | | | | |
| Myalgia | None | | | | | | | | | | | | | | | | | | |
| | Mild | | | | | | | | | | | | | | | | | | |
| | Moderate | | | | | | | | | | | | | | | | | | |
| | Severe | | | | | | | | | | | | | | | | | | |
| Nausea | None | | | | | | | | | | | | | | | | | | |
| | Mild | | | | | | | | | | | | | | | | | | |
| | Moderate | | | | | | | | | | | | | | | | | | |
| | Severe | | | | | | | | | | | | | | | | | | |
| Any Local Symptom | None | | | | | | | | | | | | | | | | | | |
| | Mild | | | | | | | | | | | | | | | | | | |
| | Moderate | | | | | | | | | | | | | | | | | | |
| | Severe | | | | | | | | | | | | | | | | | | |
| Erythema/Redness | None | | | | | | | | | | | | | | | | | | |
| | Mild | | | | | | | | | | | | | | | | | | |

| | | Arm 2A (N=X) | | Arm 2B (N=X) | | Arm 2C (N=X) | | Arm 2D (N=X) | | Arm 2E (N=X) | | Arm 2F (N=X) | | Arm 2G (N=X) | | Arm 2H (N=X) | | All Subjects (N=X) | |
|---|----------|-----------------|---|-----------------|---|-----------------|---|-----------------|---|-----------------|---|-----------------|---|-----------------|---|-----------------|---|--------------------------|---|
| Symptom | Severity | n | % | n | % | n | % | n | % | n | % | n | % | n | % | n | % | n | % |
| | Moderate | | | | | | | | | | | | | | | | | | |
| | Severe | | | | | | | | | | | | | | | | | | |
| Erythema/Redness Measurement (mm) | None | | | | | | | | | | | | | | | | | | |
| | Mild | | | | | | | | | | | | | | | | | | |
| | Moderate | | | | | | | | | | | | | | | | | | |
| | Severe | | | | | | | | | | | | | | | | | | |
| Induration/Swelling | None | | | | | | | | | | | | | | | | | | |
| | Mild | | | | | | | | | | | | | | | | | | |
| | Moderate | | | | | | | | | | | | | | | | | | |
| | Severe | | | | | | | | | | | | | | | | | | |
| Induration/Swelling Measurement (mm) | None | | | | | | | | | | | | | | | | | | |
| | Mild | | | | | | | | | | | | | | | | | | |
| | Moderate | | | | | | | | | | | | | | | | | | |
| | Severe | | | | | | | | | | | | | | | | | | |
| Pain | None | | | | | | | | | | | | | | | | | | |
| | Mild | | | | | | | | | | | | | | | | | | |
| | Moderate | | | | | | | | | | | | | | | | | | |
| | Severe | | | | | | | | | | | | | | | | | | |

Severity is the maximum severity reported over all solicited symptoms post dosing for each subject.
N=All subjects receiving vaccination with any solicited event data recorded in the database.

Table 390: Summary of Solicited Events by Days Post Dose 1, Symptom, and Treatment Group – Treatment Arm 2A (Three Vaccinations)

| | | Pre-Dose (N=X) | | Post-Dose (N=X) | | Day 1 (N=X) | | Day 2 (N=X) | | Day 3 (N=X) | | Day 4 (N=X) | | Day 5 (N=X) | | Day 6 (N=X) | | Day 7 (N=X) | | Day 8+ ¹ (N=X) | | Any Post-Dose ² | |
|----------------------|----------|-------------------|---|--------------------|---|----------------|---|----------------|---|----------------|---|----------------|---|----------------|---|----------------|---|----------------|---|------------------------------|---|-------------------------------|---|
| Symptom | Severity | n | % | n | % | n | % | n | % | n | % | n | % | n | % | n | % | n | % | n | % | n | % |
| Any Symptom | None | | | | | | | | | | | | | | | | | | | | | | |
| | Mild | | | | | | | | | | | | | | | | | | | | | | |
| | Moderate | | | | | | | | | | | | | | | | | | | | | | |
| | Severe | | | | | | | | | | | | | | | | | | | | | | |
| Any Systemic Symptom | None | | | | | | | | | | | | | | | | | | | | | | |
| | Mild | | | | | | | | | | | | | | | | | | | | | | |
| | Moderate | | | | | | | | | | | | | | | | | | | | | | |
| | Severe | | | | | | | | | | | | | | | | | | | | | | |
| Arthralgia | None | | | | | | | | | | | | | | | | | | | | | | |
| | Mild | | | | | | | | | | | | | | | | | | | | | | |
| | Moderate | | | | | | | | | | | | | | | | | | | | | | |
| | Severe | | | | | | | | | | | | | | | | | | | | | | |
| Fatigue | None | | | | | | | | | | | | | | | | | | | | | | |
| | Mild | | | | | | | | | | | | | | | | | | | | | | |
| | Moderate | | | | | | | | | | | | | | | | | | | | | | |
| | Severe | | | | | | | | | | | | | | | | | | | | | | |
| Fever | None | | | | | | | | | | | | | | | | | | | | | | |
| | Mild | | | | | | | | | | | | | | | | | | | | | | |
| | Moderate | | | | | | | | | | | | | | | | | | | | | | |
| | Severe | | | | | | | | | | | | | | | | | | | | | | |
| Feverishness | None | | | | | | | | | | | | | | | | | | | | | | |
| | Mild | | | | | | | | | | | | | | | | | | | | | | |

| Symptom | Severity | Pre-Dose (N=X) | | Post-Dose (N=X) | | Day 1 (N=X) | | Day 2 (N=X) | | Day 3 (N=X) | | Day 4 (N=X) | | Day 5 (N=X) | | Day 6 (N=X) | | Day 7 (N=X) | | Day 8+ ¹ (N=X) | | Any Post-Dose ² | | |
|-------------------|----------|----------------|---|-----------------|---|-------------|---|-------------|---|-------------|---|-------------|---|-------------|---|-------------|---|-------------|---|---------------------------|---|----------------------------|---|--|
| | | n | % | n | % | n | % | n | % | n | % | n | % | n | % | n | % | n | % | n | % | n | % | |
| | Moderate | | | | | | | | | | | | | | | | | | | | | | | |
| | Severe | | | | | | | | | | | | | | | | | | | | | | | |
| Headache | None | | | | | | | | | | | | | | | | | | | | | | | |
| | Mild | | | | | | | | | | | | | | | | | | | | | | | |
| | Moderate | | | | | | | | | | | | | | | | | | | | | | | |
| | Severe | | | | | | | | | | | | | | | | | | | | | | | |
| Myalgia | None | | | | | | | | | | | | | | | | | | | | | | | |
| | Mild | | | | | | | | | | | | | | | | | | | | | | | |
| | Moderate | | | | | | | | | | | | | | | | | | | | | | | |
| | Severe | | | | | | | | | | | | | | | | | | | | | | | |
| Nausea | None | | | | | | | | | | | | | | | | | | | | | | | |
| | Mild | | | | | | | | | | | | | | | | | | | | | | | |
| | Moderate | | | | | | | | | | | | | | | | | | | | | | | |
| | Severe | | | | | | | | | | | | | | | | | | | | | | | |
| Any Local Symptom | None | | | | | | | | | | | | | | | | | | | | | | | |
| | Mild | | | | | | | | | | | | | | | | | | | | | | | |
| | Moderate | | | | | | | | | | | | | | | | | | | | | | | |
| | Severe | | | | | | | | | | | | | | | | | | | | | | | |
| Erythema/Redness | None | | | | | | | | | | | | | | | | | | | | | | | |
| | Mild | | | | | | | | | | | | | | | | | | | | | | | |
| | Moderate | | | | | | | | | | | | | | | | | | | | | | | |
| | Severe | | | | | | | | | | | | | | | | | | | | | | | |
| | None | | | | | | | | | | | | | | | | | | | | | | | |

| Symptom | Severity | Pre-Dose (N=X) | | Post-Dose (N=X) | | Day 1 (N=X) | | Day 2 (N=X) | | Day 3 (N=X) | | Day 4 (N=X) | | Day 5 (N=X) | | Day 6 (N=X) | | Day 7 (N=X) | | Day 8+ ¹ (N=X) | | Any Post-Dose ² | | |
|--------------------------------------|----------|----------------|---|-----------------|---|-------------|---|-------------|---|-------------|---|-------------|---|-------------|---|-------------|---|-------------|---|---------------------------|---|----------------------------|---|--|
| | | n | % | n | % | n | % | n | % | n | % | n | % | n | % | n | % | n | % | n | % | n | % | |
| Erythema/Redness Measurement (mm) | Mild | | | | | | | | | | | | | | | | | | | | | | | |
| | Moderate | | | | | | | | | | | | | | | | | | | | | | | |
| | Severe | | | | | | | | | | | | | | | | | | | | | | | |
| Induration/Swelling | None | | | | | | | | | | | | | | | | | | | | | | | |
| | Mild | | | | | | | | | | | | | | | | | | | | | | | |
| | Moderate | | | | | | | | | | | | | | | | | | | | | | | |
| | Severe | | | | | | | | | | | | | | | | | | | | | | | |
| Induration/Swelling Measurement (mm) | None | | | | | | | | | | | | | | | | | | | | | | | |
| | Mild | | | | | | | | | | | | | | | | | | | | | | | |
| | Moderate | | | | | | | | | | | | | | | | | | | | | | | |
| | Severe | | | | | | | | | | | | | | | | | | | | | | | |
| Pain | None | | | | | | | | | | | | | | | | | | | | | | | |
| | Mild | | | | | | | | | | | | | | | | | | | | | | | |
| | Moderate | | | | | | | | | | | | | | | | | | | | | | | |
| | Severe | | | | | | | | | | | | | | | | | | | | | | | |

Notes: N=Number of subjects in the Safety Population.
 Severity is the maximum severity reported post dosing for each subject for each day.
¹ Day 8+ includes the maximum severity of each symptom reported on or after Day 8 (includes ongoing symptoms)
² Indicates how many subjects had “None”, “Mild”, “Moderate”, or “Severe” as their maximum severity for any day. A subject may be counted in more than one of these categories.

Tables with Similar Format:

[Implementation note: For any symptoms or days with missing data, add a “Not Reported” row.]

- Table 391: Summary of Solicited Events by Days Post Dose 2, Symptom, and Treatment Group – Treatment Arm 2A (Three Vaccinations)**
- Table 392: Summary of Solicited Events by Days Post Dose 3, Symptom, and Treatment Group – Treatment Arm 2A (Three Vaccinations)**
- Table 393: Summary of Solicited Events by Days Post Dose 1, Symptom, and Treatment Group – Treatment Arm 2B (Three Vaccinations)**
- Table 394: Summary of Solicited Events by Days Post Dose 2, Symptom, and Treatment Group – Treatment Arm 2B (Three Vaccinations)**
- Table 395: Summary of Solicited Events by Days Post Dose 3, Symptom, and Treatment Group – Treatment Arm 2B (Three Vaccinations)**
- Table 396: Summary of Solicited Events by Days Post Dose 1, Symptom, and Treatment Group – Treatment Arm 2C (Two Vaccinations)**
- Table 397: Summary of Solicited Events by Days Post Dose 2, Symptom, and Treatment Group – Treatment Arm 2C (Two Vaccinations)**
- Table 398: Summary of Solicited Events by Days Post Dose 1, Symptom, and Treatment Group – Treatment Arm 2D (Two Vaccinations)**
- Table 399: Summary of Solicited Events by Days Post Dose 2, Symptom, and Treatment Group – Treatment Arm 2D (Two Vaccinations)**
- Table 400: Summary of Solicited Events by Days Post Dose 1, Symptom, and Treatment Group – Treatment Arm 2E (Two Vaccinations)**
- Table 401: Summary of Solicited Events by Days Post Dose 2, Symptom, and Treatment Group – Treatment Arm 2E (Two Vaccinations)**
- Table 402: Summary of Solicited Events by Days Post Dose 1, Symptom, and Treatment Group – Treatment Arm 2F (Two Vaccinations)**
- Table 403: Summary of Solicited Events by Days Post Dose 2, Symptom, and Treatment Group – Treatment Arm 2F (Two Vaccinations)**
- Table 404: Summary of Solicited Events by Days Post Dose 1, Symptom, and Treatment Group – Treatment Arm 2G (Two Vaccinations)**
- Table 405: Summary of Solicited Events by Days Post Dose 2, Symptom, and Treatment Group – Treatment Arm 2G (Two Vaccinations)**
- Table 406: Summary of Solicited Events by Days Post Dose 1, Symptom, and Treatment Group – Treatment Arm 2H (Two Vaccinations)**
- Table 407: Summary of Solicited Events by Days Post Dose 2, Symptom, and Treatment Group – Treatment Arm 2H (Two Vaccinations)**

Table 408: Summary of Number of Days of Solicited Symptoms by Treatment Group - All Subjects

| Variable | Statistic | Arm 2A (N=X) | Arm 2B (N=X) | Arm 2C (N=X) | Arm 2D (N=X) | Arm 2E (N=X) | Arm 2F (N=X) | Arm 2G (N=X) | Arm 2H (N=X) | All Subjects (N=X) |
|-----------------------------|--------------------|-----------------|-----------------|-----------------|-----------------|-----------------|-----------------|-----------------|-----------------|-----------------------|
| Any Symptom | n | | | | | | | | | |
| | Mean | | | | | | | | | |
| | Standard Deviation | | | | | | | | | |
| | Median | | | | | | | | | |
| | Minimum | | | | | | | | | |
| | Maximum | | | | | | | | | |
| Any Systemic Symptom | n | | | | | | | | | |
| | Mean | | | | | | | | | |
| | Standard Deviation | | | | | | | | | |
| | Median | | | | | | | | | |
| | Minimum | | | | | | | | | |
| | Maximum | | | | | | | | | |
| Arthralgia | n | | | | | | | | | |
| | Mean | | | | | | | | | |
| | Standard Deviation | | | | | | | | | |
| | Median | | | | | | | | | |
| | Minimum | | | | | | | | | |
| | Maximum | | | | | | | | | |
| Fatigue | n | | | | | | | | | |
| | Mean | | | | | | | | | |

| Variable | Statistic | Arm 2A (N=X) | Arm 2B (N=X) | Arm 2C (N=X) | Arm 2D (N=X) | Arm 2E (N=X) | Arm 2F (N=X) | Arm 2G (N=X) | Arm 2H (N=X) | All Subjects (N=X) |
|---------------------|--------------------|-----------------|-----------------|-----------------|-----------------|-----------------|-----------------|-----------------|-----------------|-----------------------|
| | Standard Deviation | | | | | | | | | |
| | Median | | | | | | | | | |
| | Minimum | | | | | | | | | |
| | Maximum | | | | | | | | | |
| Fever | n | | | | | | | | | |
| | Mean | | | | | | | | | |
| | Standard Deviation | | | | | | | | | |
| | Median | | | | | | | | | |
| | Minimum | | | | | | | | | |
| | Maximum | | | | | | | | | |
| Feverishness | n | | | | | | | | | |
| | Mean | | | | | | | | | |
| | Standard Deviation | | | | | | | | | |
| | Median | | | | | | | | | |
| | Minimum | | | | | | | | | |
| | Maximum | | | | | | | | | |
| Headache | n | | | | | | | | | |
| | Mean | | | | | | | | | |
| | Standard Deviation | | | | | | | | | |
| | Median | | | | | | | | | |
| | Minimum | | | | | | | | | |
| | Maximum | | | | | | | | | |

| Variable | Statistic | Arm 2A (N=X) | Arm 2B (N=X) | Arm 2C (N=X) | Arm 2D (N=X) | Arm 2E (N=X) | Arm 2F (N=X) | Arm 2G (N=X) | Arm 2H (N=X) | All Subjects (N=X) |
|--------------------------|--------------------|-----------------|-----------------|-----------------|-----------------|-----------------|-----------------|-----------------|-----------------|-----------------------|
| Myalgia | n | | | | | | | | | |
| | Mean | | | | | | | | | |
| | Standard Deviation | | | | | | | | | |
| | Median | | | | | | | | | |
| | Minimum | | | | | | | | | |
| | Maximum | | | | | | | | | |
| Nausea | n | | | | | | | | | |
| | Mean | | | | | | | | | |
| | Standard Deviation | | | | | | | | | |
| | Median | | | | | | | | | |
| | Minimum | | | | | | | | | |
| | Maximum | | | | | | | | | |
| Any Local Symptom | n | | | | | | | | | |
| | Mean | | | | | | | | | |
| | Standard Deviation | | | | | | | | | |
| | Median | | | | | | | | | |
| | Minimum | | | | | | | | | |
| | Maximum | | | | | | | | | |
| Erythema/redness | n | | | | | | | | | |
| | Mean | | | | | | | | | |
| | Standard Deviation | | | | | | | | | |
| | Median | | | | | | | | | |

| Variable | Statistic | Arm 2A (N=X) | Arm 2B (N=X) | Arm 2C (N=X) | Arm 2D (N=X) | Arm 2E (N=X) | Arm 2F (N=X) | Arm 2G (N=X) | Arm 2H (N=X) | All Subjects (N=X) |
|--|--------------------|-----------------|-----------------|-----------------|-----------------|-----------------|-----------------|-----------------|-----------------|-----------------------|
| | Minimum | | | | | | | | | |
| | Maximum | | | | | | | | | |
| Induration/swelling | n | | | | | | | | | |
| | Mean | | | | | | | | | |
| | Standard Deviation | | | | | | | | | |
| | Median | | | | | | | | | |
| | Minimum | | | | | | | | | |
| | Maximum | | | | | | | | | |
| Pain | n | | | | | | | | | |
| | Mean | | | | | | | | | |
| | Standard Deviation | | | | | | | | | |
| | Median | | | | | | | | | |
| | Minimum | | | | | | | | | |
| | Maximum | | | | | | | | | |
| Notes: N=Number of subjects in the Safety Population. n=Number of solicited adverse events. | | | | | | | | | | |

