3. STUDY OBJECTIVES AND ENDPOINTS

3.1. Study Objectives and Endpoints

| OBJECTIVES | ENDPOINTS (OUTCOME MEASURES) |
|--|--|
| Primary | |
| 
 To evaluate the safety and reactogenicity of mRNA-1273 and mRNA-1273.351 vaccines, in naïve individuals. | 
 Frequency and grade of each solicited local and systemic reactogenicity AE during a 7-day follow-up period post each vaccination. Frequency and grade of any unsolicited AEs during the 28-day follow-up period post each vaccination. Frequency of any SAEs, Protocol Specified AESIs, NOCMCs, and MAAEs from the first vaccination through 12 months after the last vaccination. |
| Secondary | |
| 
 To assess humoral immunogenicity of mRNA-1273 and mRNA-1273.351 vaccines, in naïve individuals. | 
 Response rate, and magnitude of SARS-CoV-2-specific antibody binding and neutralization titers in serum samples as assessed via a range of assays at all timepoints. |
| Exploratory | |
| 
 To assess, in at least a subset of samples the innate immune response and B cell response following vaccination. | 
 Magnitude, phenotype, and percentage of innate immune cells and SARS-CoV-2 specific B cells, as measured by flow cytometry, and targeted B cell repertoire analysis at different timepoints post vaccination relative to baseline. |
| 
 To assess, in at least a subset of samples, the SARS-CoV-2 S protein-specific T cell responses. | 
 Magnitude, phenotype, and percentage of cytokine producing S protein-specific T cells, as measured by flow cytometry at different timepoints post vaccination relative to baseline. |

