Subjects in Cohort 1 will receive a single intramuscular (IM) injection of the designated vaccine and will be followed through 12 months after vaccination. Follow-up visits will occur on Days 8, 15, and 29, as well as 3, 6, and 12 months after the vaccination.

Cohort 2 will include approximately 150 participants 18 through 55 years of age who have not received a COVID-19 vaccine, have no known history of COVID-19 or SARS-CoV-2 infection, and do not have underlying conditions that are associated with an increased risk of severe illness from SARS-CoV-2 infection. Enrollment may close before the full 150 participants based on estimates on the timing of immunogenicity results and the need to inform public health decisions. They will be randomly assigned to one of 8 treatment arms and will receive 2 or 3 IM injections of the vaccine and followed through 12 months after the last vaccination ([Table 1](#)).

Follow-up visits will occur 7, 14, and 28 days after each vaccination, as well as 3, 6, and 12 months post the last vaccination.

For both Cohorts 1 and 2, reactogenicity will be assessed and blood will be drawn for immunogenicity assays.

After the IND is in effect, IRB review and approval, and site activation, the participating sites will begin recruitment outreach efforts, which can include fliers, letters, telephone calls, etc. Information regarding this trial may be provided to potential subjects who have previously participated in other vaccine trials conducted at the participating site. Other forms and/or mechanisms of recruitment may also be used. The IRB will approve the recruitment process and all materials prior to use. Screening can occur up to 42 days prior to the first dose.

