9. SAFETY EVALUATION

Summaries and analysis of safety data will be presented for the Safety Analysis Population.

Solicited AEs will be summarized by severity for each day post vaccination (Days 1-8) for each dose and as the maximum severity over all 8 days. Additionally, solicited AEs will be analyzed by taking the most severe response over the follow-up period and using standard techniques, such as exact confidence intervals (CI), to summarize the proportion of subjects reporting each symptom, any local symptom, and any systemic symptom.

Unsolicited non-serious AEs will be collected from the time of the first vaccination through 28 days after the final vaccination. Unsolicited AEs will be coded by MedDRA for preferred term and system organ class (SOC). SAEs, Protocol Specified AESIs, MAAEs, and NOCMCs will be collected from the time of first vaccination through 12 months after the final vaccination. The numbers of SAEs and MAAEs will be reported by detailed listings showing the event description, MedDRA preferred term and SOC, relevant dates (vaccinations and AEs), severity, relatedness, and outcome for each event. Non-serious unsolicited AEs will be summarized as number and percentage of subjects reporting at least one event in each MedDRA preferred term and SOC, cross tabulated by severity and relationship to study product. Additionally, the proportion of subjects and exact 95% CIs of AEs in aggregate and by MedDRA categories will be computed.

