9.3.1. Solicited Events and Symptoms

Systemic solicited adverse events were collected pre-vaccination, and systemic and local solicited adverse events were collected 30 minutes post-vaccination and then daily for 7 days after the vaccination and graded on a scale of 0 (absent), 1 (mild), 2 (moderate) and 3 (severe). Systemic events include: fatigue, headache, myalgia, arthralgia, nausea, chills and fever. Local events include: pain at injection site, erythema, and induration.

For each systemic and local event, any systemic event, any local event, and any solicited event, the maximum severity over 7 days after the third vaccination will be summarized for the Safety population. The number and percentage of subjects reporting each event will be summarized by the maximum severity and treatment group (Table 389). For each event the denominator is the number of subjects with non-missing data for the specific event.

The number of subjects reporting a solicited adverse event will be summarized for each day post-vaccination both in a summary table (starting with Table 390 and ending with Table 407) and graphically in a bar chart (Figure 1250, Figure 1251, Figure 1252, Figure 1253, Figure 1254, and Figure 1255).

The mean, standard deviation, median, minimum and maximum duration of solicited events will be summarized (Table 408).

Day of solicited symptom onset will be summarized graphically (Figure 1256, Figure 1257, Figure 1258, Figure 1259, Figure 1260, and Figure 1261).

Solicited adverse events by subject will be presented in listings (Listing 10 and Listing 11) and graphically (starting with Figure 1262 and ending with Figure 1275).

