- f) Visits 08-13 windows should be based off the actual Visit 07 date.
- g) Collect Memory Aid and assess for delayed onset local reactions.

Table 3: Schedule of Study Procedures for Treatment Arms 2C-H (Two Vaccinations)

| Study Day | -42 to -1 | 1 | 8* | 15 | 29 | 36* | 43 | 57 | 119 | 209 | 394 | Unsc Visit | Early Term Visit |
|--|-------------------------|----------------|----|----------------|----|-----------------|-----------------|-----------------|-----------------|-----------------|-----------------|------------|------------------|
| Visit Window (±number of days) | | 0 | 1 | 2 | 2 | 1 | 2 | 2 | 7 | 7 | 14 | | |
| Study Visit | Screening (optional) 00 | 01 | 02 | 03 | 04 | 05 ^e | 06 ^e | 07 ^e | 08 ^e | 09 ^e | 10 ^e | | |
| Informed Consent | X | X ^a | | | | | | | | | | | |
| Review Eligibility Criteria | X | X | | | | | | | | | | | |
| Medical History | X | X ^a | | | | | | | | | | | |
| Vaccination | | X | | | X | | | | | | | | |
| Concomitant Medications | | X | X | X | X | X | X | X | | | | | |
| Interim History | | X ^b | | X | X | | X | X | X | X | X | X | X |
| Symptom-Directed Physical Examination | X | X | | X | X | | X | X | X | X | X | X | X |
| Vital Signs ^c | | X | | X | X | | X | X | X | X | X | X | X |
| Height and Weight (for BMI) | X | X ^a | | | | | | | | | | | |
| Pregnancy Test ^d | | X | | | X | | | | | | | | |
| Memory Aid: Solicited AEs | | X | X | X ^f | X | X | X ^f | | | | | | |
| Unsolicited AEs | | X | X | X | X | X | X | X | | | | | |
| SAEs, Protocol Specified AESIs, MAAEs, and NOCMCs | | X | X | X | X | X | X | X | X | X | X | X | X |
| Serum for Serological Immunogenicity Assays | | X | | X | X | | X | X | X | X | X | | X |
| Peripheral Blood Mononuclear Cells (PBMCs) for Cellular Immunology Assays (and Plasma) | | X | | X | X | | X | | | X | X | | X |

* Telephone call.

- a) If not performed at Visit 00.
- b) If medical history performed at Visit 00, then interim history at Visit 01.
- c) Vital signs to be obtained pre and post vaccination. Otherwise, only as clinically indicated.
- d) For women of childbearing potential, a negative urine pregnancy test on Day 1 with results confirmed prior to enrollment.
- e) Visits 05-10 windows should be based off the actual Visit 04 date.
- f) Collect Memory Aid and assess for delayed onset local reactions.

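### Tables 390-407 do not give each subject's maximum solicited-AE severity over the 7-day window for each dose

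*SAP*

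**What the plan says.** SAP Section 3.1 makes the first primary endpoint "Frequency and grade of each solicited local and systemic reactogenicity AE during a 7-day follow-up period post each vaccination". Section 9 says that severity will be summarized "for each day post vaccination (Days 1-8) for each dose and as the maximum severity over all 8 days". Section 9.3.1 describes the data as "collected 30 minutes post-vaccination and then daily for 7 days after the vaccination".

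The displays that carry this by dose are Tables 390-407. Table 390 is drawn in full and the others share its format. Its columns are Pre-Dose, Post-Dose, Day 1 to Day 7, Day 8+ and Any Post-Dose. Footnote 1 reads "Day 8+ includes the maximum severity of each symptom reported on or after Day 8 (includes ongoing symptoms". Footnote 2 describes Any Post-Dose as the number of subjects with each severity "as their maximum severity for any day. A subject may be counted in more than one of these categories".

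Table 389 is the other table of solicited severity. For it, Section 9.3.1 says "the maximum severity over 7 days after the third vaccination will be summarized for the Safety population". Its table note speaks only of the period after dosing, with no dose and no number of days.

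The schedules of procedures (Table 2 footnote g, Table 3 footnote f) add, at the visit 14 days after each dose, "Collect Memory Aid and assess for delayed onset local reactions".

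**The concern.** The text fixes a closed window and a single summary per subject and dose, but the shells do neither. Day 8 has no column of its own. The summary column has no cut-off, and it can place one subject in several severity rows. A programmer who follows the shells will not produce the statistic that Sections 3.1 and 9 describe, and this is a primary endpoint. A reader of the report could also take Any Post-Dose for the 7-day result.

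**Working it through.** **1. Day count.** Section 4.1 states "Follow-up visits will occur 7, 14, and 28 days after each vaccination", and Tables 2 and 3 put vaccinations on Days 1, 29 and (Arms 2A-B) 57. Adding 7 gives 1 + 7 = 8, 29 + 7 = 36 and 57 + 7 = 64, which are the telephone-call days in those schedules. With vaccination on Day 1, the window is Days 1-8, or 8 calendar days. This reproduces Section 9's figure.

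**2. Coverage.** Two arms with 3 doses and six arms with 2 doses give 2 × 3 + 6 × 2 = 18 tables, which matches 407 − 390 + 1 = 18. Every arm and dose has a table. Each shows 7 of the 8 window days singly and merges the eighth with everything later.

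**3. Three hypothetical subjects** (0 = none, 1 = mild, 2 = moderate), vaccination day = Day 1. A is moderate on Day 8 only. B has a new moderate reaction on Day 10. C is mild on Day 8 and moderate on Day 9. Any Post-Dose is shown as the highest grade.

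| Subject | Days 1-7 | Day 8+ | Any Post-Dose | Max Days 1-8 | After Day 8 |
|---|---|---|---|---|---|
| A | all 0 | 2 | 2 | 2 | 0 |
| B | all 0 | 2 | 2 | 0 | 2 |
| C | all 0 | 2 | 2 | 1 | 2 |

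The planned columns are identical for all three, while the true window maxima are 2, 0 and 1. A against C needs only an ongoing symptom, which footnote 1 expressly includes. B also requires that a late-onset reaction is recorded as solicited.

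**4. Footnote 2.** Each of these subjects also has symptom-free days, so the rule would count each under None as well as Moderate. The Severe row is not distorted by this, because nothing ranks above it. The None, Mild and Moderate rows are not maximum-severity counts.

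**5. Can the maximum be rebuilt from the daily columns?** No. The number of subjects with a given grade on at least one day is at least the largest daily count and at most the sum of the daily counts (or the arm size, if smaller). Daily totals do not fix it within those bounds.

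**6. Other tables.** Table 389 in the text covers a dose that six of the eight arms (2C-H) never receive; in its note it has no dose split and no window. Table 387 counts subjects with any local or systemic solicited event, without grade, dose or window. Table 408 gives durations.

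**7. Conditional size.** If one subject's late severe report enters Any Post-Dose, the severe rate for that dose rises by 1/20 = 5.0 percentage points (Arms 2C-H) or 1/15 = 6.7 (Arms 2A-B), with no change in the 7-day rate.

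**The case against.** The best counter-argument concerns numbering. The tables are laid out by days post dose and have a separate Post-Dose column. One 30-minute reading plus seven daily readings fits Post-Dose plus Days 1-7 exactly. On that count the whole window is already shown day by day and Day 8+ lies outside it. This reading is tenable, and the SAP does not settle it. It does not rescue the shells: the labels then conflict with Section 9's Days 1-8, Any Post-Dose still has no cut-off, and the per-dose maximum is still missing.

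Three stronger readings are tempting, and the SAP does not support them.

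- A reader might infer that the 7-day endpoint cannot be read at all. Days 1-7 remain legible by day, and by-subject Listings 10 and 11 are planned.
- A reader might infer that delayed local reactions are hidden. Onset-day figures (1256-1261) are planned as well as the listings. Their mock-ups were not available for this review, so it cannot be said that no display separates late onset.
- A reader might infer that a severe reaction starting on Day 10 certainly counts in Any Post-Dose, or that Day 8+ spans 21 days (Day 8 to Day 28). The SAP does not say whether such a reaction is recorded as solicited or unsolicited, and that rule may sit in the protocol. Memory Aid collection at the 14-day visit argues against the longer span. That Day 8+ feeds Any Post-Dose is itself an inference from the column heading and footnote 2, though the natural one.

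**Conclusion.** The point holds as a mismatch between the text and the shells on a primary endpoint. Sections 3.1 and 9 specify a per-dose summary over a closed 7-day window; Tables 390-407 give an unbounded last column and an unbounded summary in which subjects can be counted more than once. No table shell shown supplies each subject's maximum over Days 1-8 for each dose. This conclusion survives either day-numbering convention.

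What is lost is limited to the summary maximum and, with vaccination as Day 1, Day 8 by itself. The 5.0 and 6.7 points are illustrations. They assume that one late severe report is recorded as solicited and enters Any Post-Dose; they are not estimates of expected bias. The change should be made before the tables are programmed.

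**What to change.** - State whether Day 1 in Tables 390-407 is the vaccination day, and use the same window and labels in Sections 9 and 9.3.1 and in the shells.
- Split Day 8+ into Day 8 and After Day 8.
- Replace or supplement Any Post-Dose with a column headed Maximum severity, Days 1-8, counting each subject once per symptom at the highest grade. Drop or reword footnote 2 accordingly.
- Keep any solicited local reaction with onset after Day 8 out of that maximum, and show it apart from symptoms ongoing from the window.

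If the other day count is adopted, the same columns apply with the labels shifted. The cost is table-shell and programming work only: daily severities are already tabulated, onset day is already planned for Figures 1256-1261, and no new data collection is needed.
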